**A Randomized Controlled Trial Testing the Efficacy of Brief Messages to Correct Misperceptions About Nicotine**

**NCT05129592**

**IRB approved 8/4/2021**

**Abstract:** Despite the known dangers of smoking and the common desire to quit millions of Americans continue to smoke cigarettes, demonstrating the need for additional interventions. Noncombustible nicotine products expose users to fewer and/or lower levels of harmful constituents, and may have lower disease risk compared to combustible cigarettes. Alternatively, very low nicotine products, such as very low nicotine cigarettes (VLNC), might reduce dependence and aid cessation. In 2019, FDA started authorizing such products to use modified risk or modified exposure marketing claims if manufacturers demonstrated a benefit to population health. The misperception that nicotine is a major cause of cancer is common and may relate to inaccurate relative harm perceptions about tobacco products. This study used strategies identified in the literature to mitigate the continued influence of misinformation in messages about the role of nicotine in tobacco products as well as product relative risk compared to smoking cigarettes to assess changes in beliefs about nicotine and relative harm as well as intention to switch to noncombustible products among adults who smoke cigarettes.

**Objectives:** The study tested the combined use of two strategies for correcting misinformation: an explicit reason for why the misinformation came to be believed and a causal alternative to replace the retracted misinformation, in messages correcting the misperception that nicotine causes cancer. Outcomes of interest included beliefs that nicotine is a cause of cancer, relative harm beliefs comparing other tobacco products to cigarettes, and intention to switch to a noncombustible product.

**Background:** The persistence of misperception has been noted in other disciplines, including cognitive psychology and political science. Many experiments in these fields have demonstrated that exposure to corrective information can elicit correct recall of the corrective information, however, misinformation is often still used to make inferences about related topics, which has come to be known as the Continued Influence Effect (CIE). It has been theorized that, when presented with corrective messaging, individuals may engage in ‘surface updating’ (the individual updates only the specific misperception addressed in the message), but fail to engage in ‘global updating’ (fully integrating information into beliefs so it can be applied via inferential reasoning and behavioral decisions). Thus, it is possible that after exposure to corrective information about nicotine, an individual could accurately state that nicotine is not the main cancer-causing constituent in tobacco (surface updating), yet fail to accurately characterize the relative harm of a non-combustible nicotine-containing product when compared to a combustible cigarette if that product was not discussed in the message (global updating).

Maintaining ‘coherence’ in a corrective message may help mitigate the CIE. Coherence refers to the explanatory power inherent in communicating the causal relationship between two things. Coherence can be achieved in correctives by providing a causal alternative - [it’s the toxicants generated during combustion, not nicotine, that are responsible for most disease risk from tobacco] – to fill the gap left by retracted information [nicotine does not cause cancer]. Causal alternatives may be important because identifying and understanding causal relationships is necessary for constructing meaning and representing information in memory. A second strategy involves providing a reason the misinformation first came to be believed, which can prompt individuals to evaluate the original misperception more critically, thus mitigating its effect.

## Study Procedures

Participants were recruited online using Amazon Mechanical Turk. After clicking on the tasks, participants first consented to answering questions on a screening questionnaire to determine eligibility. Eligible participants then read an informed consent for the experiment. After agreeing to participate, participants were asked questions about their sociodemographic characteristics, beliefs, behaviors, and behavioral intentions about different tobacco products. Participants were then randomized to view one of four messages using a 1:1:1:1 ratio using the “evenly present elements” option in Qualtrics. One message had only a causal alternative, one had only a reason the misinformation about nicotine causing cancer came to be believed, one have both strategies, and one had neither strategy. As randomization

was conducted in Qualtrics, both experimenters and participants were blinded to randomization. After message exposure, participants answered questions about the message and their beliefs and intentions to use different tobacco products. The survey took between 10-15 mins to complete. The study protocol was approved by the Institutional Review Board at the Johns Hopkins Bloomberg School of Public Health on August 4, 2021 (IRB00015120). No participants were removed while the study was ongoing, but responses that showed signs of being repeat responders or bots (according to metrics from survey platform Qualtrics) were later dropped from analysis.

### **Inclusion Criteria**

1. Were established smokers (smoked at least 100 cigarettes in their lifetime and currently smoked cigarettes some or all days).
2. Were 21 years of age or older (the legal age of tobacco purchase in the US).
3. Had not completed the cognitive interview during message development.
4. Rated their agreement with the following statement as at least 50 out of 100: “The substance nicotine causes cancer.”

### **Exclusion Criteria**

1. Were not established smokers (had not smoked at least 100 cigarettes in their lifetime or did not currently smoke some or all days)
2. Were under the age of 21.
3. Had completed a cognitive interview during message development.
4. Rated their agreement with the following statement as less than 50 out of 100: “The substance nicotine causes cancer.”

### **Study Statistics**

- a. Primary outcome variable
  1. Change in Accuracy of Belief That Nicotine Causes Cancer
  2. Change in Relative Harm Beliefs Regarding E-cigarettes
  3. Change in Relative Harm Beliefs Regarding NRT
  4. Change in Relative Harm Beliefs Regarding Very Low Nicotine Cigarettes
  5. Change in Inferential Beliefs Regarding Smokeless Tobacco
  6. Change in Inferential Beliefs Regarding Cigarillos
  7. Change in Beliefs About Intention to Switch Products
- b. Statistical plan: Stata version 15 was used for all statistical analyses. Fisher’s exact tests were used to assess balancing across conditions by categorical variables to account for small cell size (e.g. cell sizes with  $n < 10$ ). ANOVAs were used to assess differences in continuous variables to assess balancing. Analysis of Covariance (ANCOVA) was used to identify differences by condition in agreement that nicotine causes cancer, controlling for pre-exposure belief (RQ1a) and intention to switch to a noncombustible controlling for pre-exposure intention (H2). Post hoc testing was used to assess pairwise differences between conditions when the covariate for condition was significant at  $p < .05$ , comparing each condition to the condition with both components of coherence. Sidak’s adjustment was used to control the type I error. Research questions and hypotheses with relative harm outcomes (RQ1b-d, H1a-b) were dichotomized due to failure to meet the assumptions of ANCOVA and were analyzed using logistic regression. Responses “much more harmful,” “somewhat more harmful,” and “not less or more harmful” were considered high relative harm perceptions. Responses “somewhat less harmful” and “much less harmful” were considered low relative harm perceptions. Unadjusted regressions as well as regression adjusted for pre-message exposure beliefs and product use were run. Inclusion of pre-exposure beliefs as a covariate in the models for NRT and cigarillos resulted in unstable odds ratios due to near perfect

prediction. Pre-exposure beliefs were thus dropped in these models. Marginal estimates for each condition were calculated and plotted for all adjusted models.

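### Pairwise contrasts against the combined message (RQ1a, H2) appear to rest on one pooled ANCOVA variance, so individual contrasts are miscalibrated if arm variances differ; robust standard errors cost nothing

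*Combined protocol and SAP*

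**What the plan says.** Study Statistics, item b, gives the belief analysis: "Analysis of Covariance (ANCOVA) was used to identify differences by condition in agreement that nicotine causes cancer, controlling for pre-exposure belief (RQ1a". The same model covers "intention to switch to a noncombustible controlling for pre-exposure intention (H2". Pairwise tests are conditional: "Post hoc testing was used to assess pairwise differences between conditions when the covariate for condition was significant at" p < .05. They have a single reference arm, "comparing each condition to the condition with both components of coherence", and "Sidak’s adjustment was used to control the type I error". The section does not say how many comparisons the adjustment counts; the single reference arm implies three. It also states that marginal estimates are computed and plotted for the adjusted models.

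No variance estimator is named for either outcome, and no variance check is reported for them. The relative harm outcomes, by contrast, "were dichotomized due to failure to meet the assumptions of ANCOVA"; which assumption failed is not stated.

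On design, Study Procedures says "Participants were then randomized to view one of four messages using a 1:1:1:1 ratio". On the scale, Inclusion Criteria admits people who "Rated their agreement with the following statement as at least 50 out of 100", the item being that nicotine causes cancer. A 0-100 scale is documented only for that screening item. Its use for the post-exposure belief is a reasonable inference. No response scale is given for intention.

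**The concern.** ANCOVA in its usual form estimates one residual variance from all arms. With equal arms, the overall F test is fairly insensitive to unequal variances. A contrast between two of the four arms is not, because its true variance depends only on those two arms while its standard error borrows from all four.

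Unequal variances are plausible for belief. Entry at 50 or above truncates the baseline. A correction that persuades some readers and leaves others unmoved would spread the post-exposure scores in the arms where it works. If the combined message and one single-strategy message are those arms, their contrast has a standard error that is too small. That contrast bears on the study's stated aim of testing the two strategies together. If the compared arms are instead the less variable ones, the same contrast loses power.

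**Working it through.** **Inputs from the documents.** Four arms, 1:1:1:1; three contrasts with the combined message; Sidak adjustment; a p < .05 gate on the condition term. The documents state no sample size, SD or effect size, so there is no figure of the plan's to reproduce. Every SD, arm size and conversion rate below is an assumption.

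**Nominal level per contrast.** 1 − 0.95^(1/3) = 0.01695, two-sided critical z = 2.388.

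**Formula.** With equal arms, the true SE of a contrast divided by its pooled SE is r = √(mean variance of the two compared arms / mean variance of all four arms). The actual error is 2 × (1 − Φ(2.388 / r)).

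**Worked example.** SDs 32, 32 (compared arms) and 22, 22 (others):
- Mean variance of the compared arms: 32² = 1024.
- Mean variance of all four arms: (1024 + 484) / 2 = 754.
- r = √(1024 / 754) = 1.165, and 2.388 / 1.165 = 2.049.
- Error = 0.040.

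**Range, without the gate.** SDs in the order combined message / compared arm / other two:

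| Assumed SDs | r | Error per contrast | Multiple of 0.017 |
|---|---|---|---|
| 25/25/25/25 | 1.000 | 0.017 | 1.0 |
| 30/30/25/25 | 1.086 | 0.028 | 1.65 |
| 30/30/30/20 | 1.078 | 0.027 | 1.6 |
| 28/28/22/22 | 1.112 | 0.032 | 1.9 |
| 30/20/20/20 | 1.113 | 0.032 | 1.9 |
| 32/32/22/22 | 1.165 | 0.040 | 2.4 |
| 30/30/20/20 | 1.177 | 0.042 | 2.5 |
| 20/30/30/30 | 0.916 | 0.009 | 0.54 |
| 20/20/30/30 | 0.784 | 0.0023 | 0.14 |

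**Effect of the gate** (simulated arm means, 150 per arm, 200,000 runs). With all four means equal, the gate lowers the 30/30/20/20 rate from 0.042 to 0.030. When another arm truly differs (simulated means 50, 50, 60, 75), the gate always opens and the rate is 0.043.

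**Familywise error over the true-null contrasts, with the gate:**
- 32/32/22/22, all means equal: 0.042.
- 30/30/30/20, one arm different: 0.049.
- 30/20/20/20, one arm different: 0.054.
- 35/20/20/20, all means equal: 0.056.
- 35/20/20/20, one arm different: 0.064, the highest found.

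**Intervals.** At 32/32/22/22, a nominal 95% interval for one arm's mean with the pooled SD (√754 = 27.5) covers about 91% in a wide arm (1.96 × 27.5 / 32 = 1.68) and about 99% in a narrow one (1.96 × 27.5 / 22 = 2.45).

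**Robust alternative.** In ANCOVA simulations on a bounded 0-100 score with baseline 50 to 100, HC3 standard errors brought the ungated rate to about 0.014 to 0.021 in every SD pattern tried. In a further simulation with the gate (200 per arm; 30% of readers converted in the two compared arms, 5% in the others; 4,000 runs), the error was 4.8% pooled and 1.4% with HC3. With no variance difference the two were 1.45% and 1.4%.

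**The case against.** The strongest objection is that the plan controls familywise error, not the per-contrast 1.7%. When the two compared arms are wide and the other two truly differ, only one contrast is a true null. Its 4% error is then the whole familywise error, which is within 5%. This stands, and it sets the scale of the point.

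Second, the size depends on assumed SDs. Milder mixtures (200 per arm) gave less: about 2.6% with 15% converted in the other two arms and 30% in the compared arms, 2.3% with 20% and 30%, and 1.6% with 30% and 40%. With 40% and 70% the variance falls in the more effective arms and the error was 1.4%. So a bounded scale does not by itself produce inflation, and spread need not rise where a message works. This stands too.

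Third, the gate trims the inflation when all means are equal. True, but it gives no protection once another arm truly differs.

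A reader might infer three stronger things that the documents do not support:
- That these tests do run at two to three times their nominal level. That needs particular SD patterns, and no SDs are given.
- That both outcomes are bounded 0-100 scores. The entry threshold and the mechanism concern belief only; for H2 the general point about pooling holds, but nothing indicates which way the variances go.
- That the assumption failure for the relative harm outcomes shows unequal variances here. The failed assumption is not named, those outcomes have five ordered response categories, and no check is reported for RQ1a or H2.

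Finally, pooling is inferred from the word ANCOVA and is not stated. It remains the natural reading.

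**Conclusion.** The point holds in a limited form. If the ordinary pooled variance was used, equal allocation does not calibrate the individual contrasts with the combined message when arm variances differ. The direction can go either way: roughly 1.6 to 2.5 times the per-contrast level when the compared arms are among the wider ones, and as little as 0.14 times when they are the narrower ones. These figures rest on assumed SDs and on three comparisons in the Sidak adjustment. With six comparisons the level would be 0.0085, and the 30/30/20/20 multiple about 3.0 against that stricter level.

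This is a calibration fault in individual contrasts, p-values and intervals. It is not gross familywise failure, and nothing in the documents shows that it occurred. It is worth acting on because the contrasts concerned carry the study's main comparison and a better-calibrated method is available on the same model.

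**What to change.** For RQ1a and H2, keep the mean model but fit it as a linear regression of the post-exposure score on condition and pre-exposure score with HC3 standard errors. Take the overall test of condition, the three Sidak contrasts and any intervals on the marginal estimates from that fit. State that the Sidak adjustment counts three comparisons, report the residual SD by arm for both outcomes, and give the response scale for intention.

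The cost is one option in the Stata regression command, with no visible loss when variances are equal. Because the plan is written in the past tense, this would be a re-analysis of data already collected and should be labelled as such, with the ANCOVA results shown beside it.

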#### Risks

- a. Risks were minimal and included boredom of discomfort from answering survey questions.
- b. To mitigate this risk, participants read in the informed consent that they were free to skip any questions they didn't want to answer or quit their participation at any time.
- c. There were no unanticipated problems or deviations during data collection.

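### Should the two ANCOVAs (nicotine-cancer belief and intention to switch) also adjust for product use, as the adjusted logistic models do?

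*Combined protocol and SAP*

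**What the plan says.** The Statistical plan (Study Statistics, item b) assigns ANCOVA to two outcomes and names one covariate for each. For RQ1a it tests "differences by condition in agreement that nicotine causes cancer, controlling for pre-exposure belief (RQ1a"). For the switching outcome the wording is "and intention to switch to a noncombustible controlling for pre-exposure intention (H2"). Both are on the list of seven primary outcome variables (items 1 and 7).

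The five relative-harm outcomes (RQ1b-d, H1a-b) "were dichotomized due to failure to meet the assumptions of ANCOVA and were analyzed using logistic regression". For these, "Unadjusted regressions as well as regression adjusted for pre-message exposure beliefs and product use were run". For NRT and cigarillos the pre-exposure belief made the odds ratios unstable, and the plan reports: "Pre-exposure beliefs were thus dropped in these models". In those two models product use is the only stated covariate left.

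On timing, Study Procedures says that "participants were asked questions about their sociodemographic characteristics, beliefs, behaviors, and behavioral intentions about different tobacco products", and next that "Participants were then randomized to view one of four messages". Product use therefore appears to be a pre-randomisation variable, although the section does not name the item. The Risks section adds that participants were told "they were free to skip any questions".

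**The concern.** The plan treats product use as worth adjusting for in five primary outcomes and leaves it out of the other two, without comment. The variable seems to have been collected before randomisation, so adding it would be legitimate and cheap. For H2 there is a plausible link: someone who already uses a noncombustible product may differ in intention to switch to one. The plan does explain its other covariate departure, for NRT and cigarillos, so the silence here stands out.

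If product use predicted the post-message score well after allowing for the pre-message score, the two ANCOVAs would have wider confidence intervals and lower power than the data allow. A reader might also suspect that covariates were chosen outcome by outcome.

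**Working it through.** **1. Which models contain what.** The ANCOVA sentence lists its own covariates, and the product-use sentence comes after the logistic text. The natural reading is that product use is absent from the ANCOVAs.

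| Outcome | Model | Covariates stated for the adjusted model |
|---|---|---|
| RQ1a, nicotine-cancer belief | ANCOVA | pre-exposure belief |
| H2, intention to switch | ANCOVA | pre-exposure intention |
| E-cigarettes, very low nicotine cigarettes, smokeless tobacco | logistic | pre-exposure belief and product use |
| NRT, cigarillos | logistic | product use |

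The plan has no single covariate set from which the ANCOVAs depart. The logistic models were also run unadjusted, and the plan does not say which version is primary.

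**2. Validity.** Product use measured before randomisation is independent of message condition by design. In a linear model, omitting it leaves the condition contrasts unbiased and the test at its nominal level. Only precision can change. In a logistic model an added prognostic covariate also changes the odds ratio being estimated, so the two model types need not share a covariate list.

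**3. Size of any precision gain.** The documents give no sample size, standard deviation, power or correlation, so there is no figure of the plan's own to reproduce. All inputs below are assumptions. Let Y be the post-message score, X the pre-message score and U product use. The share of residual variance that U removes, once X is in the model, is

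R² = (r_YU − r_YX·r_XU)² / [(1 − r_YX²)(1 − r_XU²)]

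Worked example with r_YX = 0.8 and r_XU = r_YU = 0.3: (0.30 − 0.24)² / (0.36 × 0.91) = 0.0036 / 0.3276 = 1.10%.

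The standard error is multiplied by √(1 − R²), and the effective sample size by 1/(1 − R²). Power is for the 3-df condition test at two-sided 0.05, set at 80% without product use. It comes from the noncentral F distribution and is nearly the same for assumed totals of 200 to 1,600.

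| r_YX | r_XU | r_YU | R² | SE | Effective N | Power |
|---|---|---|---|---|---|---|
| 0.8 | 0.3 | 0.24 | 0 | 0 | 0 | 80.0% |
| 0.9 | 0.3 | 0.30 | 0.5% | −0.3% | +0.5% | 80.2% |
| 0.8 | 0.3 | 0.30 | 1.1% | −0.5% | +1.1% | 80.5% |
| 0.7 | 0.3 | 0.30 | 1.7% | −0.9% | +1.8% | 80.8% |
| 0.8 | 0.3 | 0.37 | 5.2% | −2.6% | +5.4% | 82.3% |
| 0.7 | 0.3 | 0.37 | 5.5% | −2.8% | +5.8% | 82.4% |
| 0.8 | 0.3 | 0.40 | 7.8% | −4.0% | +8.5% | 83.4% |
| 0.7 | 0.3 | 0.40 | 7.8% | −4.0% | +8.4% | 83.4% |

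The first row is the case r_YU = r_YX·r_XU, where product use acts only through the pre-exposure score and the gain is exactly zero. The rows above 5% require product use to predict change over a survey of 10-15 minutes, not just level, and nothing in the documents supports that.

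**4. Skipped items.** Because questions could be skipped, a complete-case model with product use gains only if the skip rate is below R². With R² = 1.1% and an assumed 2% skipped, the variance ratio is (1 − 0.011)/(1 − 0.02) = 1.009, a slight loss. A missing-category indicator would be needed to keep a gain of about 1%.

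**5. Whether adding it now would help.** The plan is written in the past tense, so the analyses appear to have been run. Product use could then only enter as a supplementary model added after the fact, with the stated ANCOVA kept as the main one. The main estimate, its confidence interval and its power would not change.

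**The case for a change.** The strongest case is H2. The outcome is about moving to a noncombustible product, current use of one is a plausible predictor, the data seem to be in hand, and the plan itself thought product use mattered for five other primaries. Extra degrees of freedom cost almost nothing: five uninformative covariates lower 80% power by at most 0.02 percentage points at a total of 200. At an assumed partial R² of 0.10 or more, power would rise by about 4 points, which is not trivial.

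The text and the arithmetic behind this case are correct. They do not show that precision was lost. The covariate usually expected to matter most, the baseline of the same outcome, is already in both models. Pre-exposure intention, asked in the same sitting, should carry much of what current use says about later intention.

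For RQ1a the case is weaker. That belief concerns a substance rather than a product. Everyone enrolled is a current smoker, so cigarette use varies little beyond some days versus all days. The entry rule of at least 50 out of 100 on this belief also truncates the scale, which could move the assumed correlations in either direction.

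A subject-matter reason for the difference is easy to see: product-specific use fits product-specific harm beliefs. The plan does not state it, and that omission stands, as does the missing definition of product use. Both are gaps in description.

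**Conclusion.** The concern does not hold. The plan does use different covariates for the ANCOVA and logistic outcomes without saying why, but both ANCOVAs adjust for the baseline of their own outcome and are valid as written. The supposed loss runs from nothing to about 8% of residual variance, or 0 to about 3.4 power points from an assumed 80%. That range rests entirely on assumed correlations (pre-post 0.7 to 0.9, product use 0.3 with the pre score and 0.24 to 0.40 with the post score). A further baseline covariate in these models is a matter of preference. The plan could define product use and say why the covariates differ, but neither point affects the validity of the two analyses.

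### Does testing the three contrasts only after a significant condition test, with the Sidak count unprinted, call for a change?

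*Combined protocol and SAP*

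**What the plan says.** Study Procedures sets out four arms: "Participants were then randomized to view one of four messages using a 1:1:1:1 ratio". The messages carry a causal alternative only, a reason for the misbelief only, both, or neither. Under Objectives, "The study tested the combined use of two strategies for correcting misinformation".

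Item b of Study Statistics gives the purpose of the ANCOVA: "Analysis of Covariance (ANCOVA) was used to identify differences by condition in agreement that nicotine causes cancer". The same model serves intention to switch, and each is adjusted for its pre-exposure value. Contrasts come second: "Post hoc testing was used to assess pairwise differences between conditions when the covariate for condition was significant at" p < .05, and that sentence ends "comparing each condition to the condition with both components of coherence". The next sentence is "Sidak’s adjustment was used to control the type I error". Whatever the condition test shows, "Marginal estimates for each condition were calculated and plotted for all adjusted models".

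The documents give no sample size, standard deviation, target effect, power, sidedness or Sidak count.

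**The concern.** Two things look wrong.

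- **The family.** Four arms make six pairs, but only three of them involve the combined message. If Sidak was applied over six, the per-contrast alpha is about half what it is over three. A reader who does not know the count cannot reproduce an adjusted p-value.
- **The gate.** A Sidak-adjusted contrast is a valid test without a preliminary 3-df test. Requiring that test as well can only withhold contrasts that would have passed, so power is spent with no evident return. The likeliest casualty is combined versus neither when each strategy contributes part of the effect, because the omnibus test is then at its weakest relative to that contrast.

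At stake are power and reproducibility. Neither point can inflate type I error within an outcome.

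**Working it through.** **Inputs.** From the documents: four equal arms, a 3-df condition test at .05, three named contrasts and a Sidak adjustment. Assumed, because the plan gives none of them: two-sided tests, adjusted SD 1, 100 to 200 per arm, large-sample distributions, and the effects shown below. There is no power or adjusted alpha in the plan to reproduce.

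**1. Critical values.** Per-contrast alpha = 1 − 0.95^(1/k).
- k = 3: 0.01695, |z| > 2.388.
- k = 6: 0.00851, |z| > 2.631.
- Gate: chi-square on 3 df > 7.815, whose square root is 2.795.

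**2. Error within one outcome** (any of the three contrasts, all arms equal).

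| Rule | No gate | With gate |
|---|---|---|
| Sidak, k = 3 | 4.5% | 3.0% |
| Sidak, k = 6 | 2.3% | 2.1% |
| No Sidak | 12.6% | 4.0% |

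When one single arm differs and the others are equal, the gate without Sidak lets error rise to about 9%. Sidak without the gate stays at about 3.3% (k = 3) or 1.7% (k = 6) at most. So Sidak does the protecting, and the gate is redundant within an outcome for either family.

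**3. What the gate costs, combined versus neither.** The 3-df statistic is the square of this contrast plus an independent 2-df remainder. A contrast is lost when |z| passes its Sidak limit but the total stays at or below 7.815. With a combined-minus-neither difference d, λ = d/√(2/n). If both single arms sit exactly halfway, the remainder carries no signal, which is the worst case.

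Example: d = 0.4, n = 100, so λ = 0.4/√0.02 = 2.828. Ungated power for k = 3 is Φ(2.828 − 2.388) = Φ(0.440) = 67.0%; gated, it is 61.0%.

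| Halfway pattern, d = 0.4, k = 3 | No gate | With gate | Loss (points) |
|---|---|---|---|
| 100 per arm | 67.0% | 61.0% | 6.0 |
| 150 per arm | 85.9% | 81.7% | 4.2 |
| 200 per arm | 94.7% | 92.5% | 2.2 |

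Over all λ the largest loss is 6.3 points, at about 56% ungated power. At 80% ungated power it is 5.0 points, and at 90% it is 3.4. Maximum losses in other patterns, k = 3: single arms at 25% and 75% of d, 3.9; only the combined message works, 2.8; only one component works, 1.7. For k = 6 the maximum in any pattern is 1.3 points.

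**4. Other targets.** For combined versus a single-strategy arm, the loss in additive patterns is at most 1.4 points. For beating all three arms it is nil. For at least one significant contrast it is larger: about 8 points (k = 3, only the combined message works, effect 0.25 or 0.3, 100 per arm).

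**5. Three or six, under the plan as written.** With the gate in place, d = 0.4, halfway pattern, 100 per arm: 61.0% (three) against 56.6% (six), a difference of 4.4 points. Without the gate the same comparison is 67.0% against 57.9%, but that is not the plan's rule.

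**6. What removing the gate costs.** Error over the two ANCOVA outcomes, if independent, is 1 − (1 − e)².
- Gated, k = 3: 1 − (1 − 0.0296)² = 5.8%.
- Ungated, k = 3: 1 − (1 − 0.045)² = 8.8%.
- For k = 6: 4.2% and 4.6%.

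**The case for a change.** The best case for a change is that it needs no new data. Stating the count takes one sentence and would make every adjusted p-value checkable. Always reporting three adjusted contrasts with simultaneous intervals keeps error within each outcome below 5%, and it recovers power that the gate gives up for no within-outcome benefit. The loss of about 8 points for at least one finding arises when only the combined message works, which bears directly on the stated objective.

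Much of this stands. The count is not printed, the gate is redundant within an outcome, and the loss is real where effects are moderate.

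It does not carry the conclusion, for three reasons. First, the sentence that mentions pairwise differences goes on to say which pairs, and Sidak follows directly, so an analyst would use three. Second, the ANCOVA's stated aim is to find differences by condition, and an overall test before contrasts is an ordinary way to serve it. Third, the plan is written in the past tense. Each condition test has already passed, in which case the gate cost nothing, or failed, in which case dropping it now would relax a conservative rule after data collection. No lost comparison is shown, and the marginal estimates are plotted either way.

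**Conclusion.** No change to the plan. The missing Sidak count is a detail that the sentence itself supplies: three contrasts, per-contrast alpha 0.01695. The gate is a fair trade-off, valid and conservative. It costs combined versus neither at most 6.3 points of power with a family of three (1.3 with six), and about 8 points for at least one significant contrast. In return it holds error over the two ANCOVA outcomes at about 5.8% rather than 8.8%, which has some value because the plan lists seven primary outcomes and states no control across them. The power figures rest on assumed arm sizes, SD and effects, and the two-outcome figures on independence. The ordering of the rules does not depend on arm size, SD or effects: adding a gate can lower power and error, but cannot raise either. This covers RQ1a and H2 only, not the five outcomes analysed by logistic regression.
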